Maintenance Phase: After the 8-week active treatment phase, participants will attend a total of 4 group-based "booster/ maintenance" sessions (according their group assignment) at 3 month intervals through the follow-up phase in order to review their use of skills/maintenance of exercise and encourage continued practice. In instances where it is deemed necessary (e.g. COVID-19 pandemic), the group based "booster/maintenance" session may be replaced with a remote visit (e.g. Skype, Zoom, MS Teams) where the trainers will contact participants and review the use of skills/maintenance of exercise and encourage continued practice. Participants randomized after 11/22/22 will complete only 2 group-based "booster/maintenance sessions due to a reduction in the scope of work in this project.

E. Treatment Integrity

Sessions will be video-recorded and an independent evaluator will review 20% of randomly selected treatment sessions from each condition and complete a treatment integrity checklist to ensure there is no "therapist drift" or contamination of treatments. Regular reviews of therapist treatment delivery will be conducted to ensure consistent implementation of the treatments across sites and monthly booster training sessions (held via conference-call format) will be held to prevent therapist drift. We have experience with this method of treatment integrity checking in our completed trials with resulting high levels of treatment fidelity.

F. Concomitant Interventions

Patients will be asked not to begin any new treatments for JFM during the active treatment phase of the study and up to the 3-month primary study end point. Medication changes during this time will be allowed *if medically necessary* and will be documented.

At baseline, patients will provide self-report data on any JFM treatments (e.g. CBT, physical therapy, acupuncture, or aquatic therapy) and the dose received in the year prior to enrollment in the study. The same information will be documented at each visit during the maintenance phase.

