Changes in prescription medication will be coded as a binary indicator of whether or not a medication change occurred. Non-pharmacologic treatments will be coded as a count variable computed as the product of frequency and duration. For example, if a participant reports receiving massage therapy twice a week (frequency) for a period of one month (duration), that participant would receive a non-pharmacologic treatment variable value of 8. For the statistical analyses that test for maintenance of treatment gains following the 3-month study intervention period, both the binary medication change variable and the non-pharmacologic treatment count variable will be entered into the longitudinal analysis model as time-varying control covariates.

G. Adherence Assessment

- a. Atttendance at treatment sessions, including make up sessions, will be recorded.
- b. Attendance to 12 out of 16 regularly scheduled sessions (i.e. 75%) will be considered receipt of full treatment per protocol.
- c. Home practice of coping skills and/or exercise will be recorded by the patients during the active treatment phase on a smart phone based application which will be modified to include these items or a paper diary, in the unlikely even that they do not have a smartphone.

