We have many procedures in place to guard against missing data including proper staff training and monitoring, as well as automated query resolution procedures for missing/inappropriate values in Medi-Data Rave[®] which will minimize missing data. However, we understand the importance of being responsive to missing data issues, and realize that the handling of missing data, including missing data due to differential drop-out raises some special considerations. We will try to obtain as much information as possible to account for missingness including reasons for drop-out. Depending on the nature of missing data, we will use strategies consistent with best statistical practice, including but not limited to multiple imputation and maximum likelihood estimation methods with auxiliary correlate variables included to make a missing at random (MAR) assumption more plausible. For example, we will use a multiple-group comparison approach with an updated estimation algorithm (i.e., MLR or WLSMV) in the most current version of MPlus that enables the proper handling of missing variable data prior to analysis. The primary analysis will be intent-to-treat analysis. However, in the case of differential attrition, if missing data not at random are suspected, sensitivity analyses under varying assumptions will also be conducted to reduce the potential for bias.

C. Analytic Plan

Analyses will be carried out on the full intent-to-treat sample as the primary analysis. Data analysis will begin with a review of all relevant variables in the dataset. For continuous variables, parametric as well as nonparametric measures of central tendency, variability, and association, will be computed. Distributional properties of potential outcomes will be evaluated and tested for normality where appropriate. Those differing markedly from normality will be considered candidates for transformation or alternative modeling techniques. Unless otherwise noted, $\alpha = 0.05$ (two-sided) will serve as the criterion for statistical significance for all analyses.

D. Rationale for analytic approach

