Significant changes in continuous FDI scores from baseline to 3-month follow-up between the FIT, CBT, and GAE groups will be tested via a longitudinal SEM approach using the current version of MPlus software. Groups will be dummy-coded with FIT as the reference class; we hypothesize significant and positive 'slope on group' coefficients for CBT and GAE indicating a significantly lower FDI for FIT vs. CBT & GAE. Non-independence of FDI scores within participant clusters and within sites will be addressed in three steps: 1.) declaring site as the complex clustering variable, and 2.) estimating a saturated patient cluster-level model (i.e., estimating all possible covariances among FDI repeated measures variances at Level 2 so that, 3.) unbiased parameter estimates and significance tests can be obtained from the longitudinal SEM growth model specified at Level 1. The primary analysis will be intent-to-treat analysis. Sensitivity analyses may also be conducted to explore the impact of the COVID-19 pandemic (those who completed treatment prior to when enrollment was suspended on March 12, 2020 and those who completed treatment after enrollment was re-initiated in Fall, 2020 with treatment delivered via remote format).

F. Aim 1b

To test whether disability levels in the FIT Teens group are maintained at lower levels than CBT alone or GAE alone over time. **H1b.** Functional disability in the FIT Teens group will remain significantly lower than CBT and GAE at 6-, 9- and 12-month follow-up.

To test whether group differences on FDI scores are maintained over time, a longitudinal SEM approach will again be used. Groups will be dummy-coded with FIT as the reference class. Significant and positive 'intercept on CBT' & 'intercept on GAE' coefficients will indicate significantly lower FDI scores for FIT vs. CBT & FIT vs GAE at 6-, 9-, & 12-month assessments. Significant and positive 'slope on CBT' & 'slope on GAE' coefficients would indicate worsening FDI scores for CBT & GAE over time relative to FIT scores that have stayed the same or further improved. Any new treatments (medications or non-pharmacologic treatments) initiated during the follow-up phase will be entered into the longitudinal analysis model as time-varying control covariates. Nesting of clustered participants within sites will be again handled with the SEM model in Mplus described above.

G. Aim 1c

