#### 6.0 Statistical Analyses

Analyses will be carried out on the full intent-to-treat sample (Sample 1) as the primary analysis. Data analysis will begin with a review of all relevant variables in the dataset. For continuous variables, parametric as well as nonparametric measures of central tendency, variability, and association, will be computed. Distributional properties of potential outcomes will be evaluated and tested for normality where appropriate. Those differing markedly from normality will be considered candidates for transformation or alternative modeling techniques. Our analyses will be divided into three distinct sections. First (Primary Aims), the effectiveness of the FIT Teens intervention (Sample 2) for the reduction of functional disability will be compared with the other two treatments in several ways. FIT Teens will be compared to a CBT-only group (Sample 3) and GAE group (Sample 4) at 3-month follow-up (H1a, H1b). Additionally, differences between groups will be compared over time (i.e., 6, 9, 12-month follow-up; H2a, H2b), and analyses will be conducted to determine whether more patients in the FIT Teens intervention group obtain clinically meaningful improvement at 3-months when compared to the other two treatments (H3a, H3b).

Second, (Secondary Aims), the effectiveness of the FIT Teens intervention (Sample 2) for the reduction of pain intensity will be compared with the other two treatments (Samples 3 and 4) in several ways, similar to FDI analyses, including comparisons at 3-month follow-up (H4a, H4b), as well as whether these treatments are sustained over time (i.e., 6, 9, 12-month follow-up; H4c, H4d). Last, exploratory analyses also will be conducted to examine a mechanistic model of physical activity. Unless otherwise noted,  $\alpha = 0.05$  (two-sided) will serve as the criterion for statistical significance for all analyses. All data will be analyzed using the current version of MPlus.

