Results will be analyzed via a longitudinal GEE approach. Groups will be dummycoded with FIT as the reference class. It is hypothesized that significant and positive 'slope on group' coefficients for CBT and GAE indicating a significantly lower FDI for FIT vs. CBT & GAE. Non-independence of FDI scores will be addressed by specifying every unique combination of participant (level 2), cohort (level 3), and site (level 4) as indicators of non-independent (correlated) responses in the GEE syntax (i.e., in the 'Repeated =' syntax specification.

- **H2a** Functional disability in the FIT Teens group will remain significantly lower than CBT at 6-, 9- and 12-month follow-up.
- **H2b** Functional disability in the FIT Teens group will remain significantly lower than GAE at 6-, 9- and 12-month follow-up.

To test whether group differences on FDI scores are maintained over time, a longitudinal SEM approach will again be used. Groups will be dummy-coded with FIT as the reference class. Significant and positive 'intercept on CBT' & 'intercept on GAE' coefficients will indicate significantly lower FDI scores for FIT vs. CBT & FIT vs GAE at 6-, 9-, & 12-month assessments. Significant and positive 'slope on CBT' & 'slope on GAE' coefficients would indicate worsening FDI scores for CBT & GAE over time relative to FIT scores that have stayed the same or further improved. Nesting of clustered participants within sites will be handled with the SEM model in Mplus described above.

- **H3a** A significantly greater proportion of the FIT Teens group will achieve clinically meaningful reduction (i.e., a decrease in at least 7.8 points) in functional disability at 3-month follow-up than CBT.
- **H3b** A significantly greater proportion of the FIT Teens group will achieve clinically meaningful reduction (i.e., a decrease in at least 7.8 points) in functional disability at 3-month follow-up than GAE.

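### Protocol and SAP disagree on whether treatments started after randomisation enter the 6- to 12-month maintenance model; if they do, the arm coefficient need not be the effect of assignment

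*Protocol*

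**What the plan says.** Protocol 5.F (Aim 1b) sets out a longitudinal SEM for FDI at 6, 9 and 12 months and adds: "Any new treatments (medications or non-pharmacologic treatments) initiated during the follow-up phase will be entered into the longitudinal analysis model as time-varying control covariates". Protocol 3.F (Concomitant Interventions) gives the same rule for the maintenance analyses, saying that "both the binary medication change variable and the non-pharmacologic treatment count variable will be entered into the longitudinal analysis model as time-varying control covariates". It also defines the two variables. For medication: "Changes in prescription medication will be coded as a binary indicator of whether or not a medication change occurred". Non-pharmacologic treatment is a count, frequency multiplied by duration. Protocol 5.H applies a similar approach to pain.

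The timing comes from protocol 3.F: patients are "asked not to begin any new treatments for JFM during the active treatment phase of the study and up to the 3-month primary study" endpoint. Medication changes are allowed in that period if medically necessary.

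The SAP opens its H2a/H2b paragraph with "To test whether group differences on FDI scores are maintained over time, a longitudinal SEM approach will again be used" and then follows the protocol paragraph closely, but the covariate sentence is absent. The pain maintenance paragraph (SAP 6.4, H4c/d) also has no such covariate. SAP 6.2 names only variables from the baseline comparisons as candidate covariates. The SAP's derived variables include medication class and counts, but neither of the two variables in protocol 3.F. SAP Table 4 nevertheless reports 6-, 9- and 12-month means adjusted for covariates that it does not name.

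On the analysis principle the documents agree. Protocol 5.C: "Analyses will be carried out on the full intent-to-treat sample as the primary analysis". SAP 6.0: "Analyses will be carried out on the full intent-to-treat sample (Sample 1) as the primary analysis".

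**The concern.** A treatment started in follow-up comes after randomisation. Because new treatments are discouraged until the 3-month endpoint, later starts come after the arms have had their effect. H1a predicts that the arms differ in disability at that point. If patients with more disability are more likely to seek further treatment (plausible, but not stated in either document), the covariate is partly a consequence of assignment. Entering it as a control then compares arms at equal later-treatment use, and can also bring in selection through unmeasured severity.

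The coding adds to the difficulty. The medication variable in 3.F records any change, so stopping a drug after improving and starting one after worsening look the same. It is also broader than the new treatments named in 5.F. The non-pharmacologic treatments that 3.F gives as examples include CBT and physical therapy, so a GAE patient who later seeks CBT is obtaining something like what that arm lacked.

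What is at stake is the interpretation of Aim 1b, which both documents list among the primary aims, and of the pain maintenance result. There is also a choice between two defensible models that could be made after the data are seen.

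**Working it through.** **1. The plan's own figure.** Protocol 5.J and SAP 4.0 assume d = 0.90 (FIT), 0.52 (CBT) and 0.40 (GAE) at 6, 9 and 12 months, standardised FDI (SD 1) and n = 105 per arm. The gaps are 0.90 - 0.52 = 0.38 and 0.90 - 0.40 = 0.50. The stated power is about 0.80 at a coefficient of 0.38. A two-mean approximation with two-sided alpha 0.05 is:

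power = Φ(δ / √(2/n) - 1.96)

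- FIT-CBT: 0.38 / √(2/105) = 2.753, and Φ(0.793) = 0.786.
- FIT-GAE: 0.50 / 0.138 = 3.623, and Φ(1.663) = 0.952.

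The figure is reproduced to within 2 points. Clustering could not be checked because no intraclass correlation is given. The power model is intercept-only with arm dummies and lists no time-varying covariate, so it matches the SAP model rather than the protocol's.

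**2. What adjustment could do.** The documents give no start rates, no dependence of starts on disability and no benefit of later treatment, so these are assumptions. The simulation had 400,000 patients, two arms, three follow-up visits, a within-person correlation of 0.6 and a gap of 0.38 SD before any new treatment. The log-odds of starting were -2.0 at average disability and rose by 0, 0.5 or 1.0 per SD of worse FDI at the previous visit. A new treatment changed FDI by 0, -0.2 or -0.4 SD. The unadjusted coefficient estimates the effect of assignment. The adjusted one adds the time-varying indicator, fitted by pooled regression or with a random intercept. Gap means adjusted minus unadjusted.

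| Log-odds per SD | Effect of new treatment | Ever started, FIT / comparator | Unadjusted | Pooled, adjusted (gap) | Random intercept, adjusted (gap) |
|---|---|---|---|---|---|
| 0 | 0 | 0.32 / 0.32 | 0.380 | 0.380 (0) | 0.380 (0) |
| 0 | -0.2 | 0.32 / 0.32 | 0.377 | 0.377 (0) | 0.377 (0) |
| 0 | -0.4 | 0.32 / 0.32 | 0.377 | 0.377 (0) | 0.377 (0) |
| 0.5 | 0 | 0.34 / 0.38 | 0.382 | 0.371 (-0.011) | 0.379 (-0.003) |
| 0.5 | -0.2 | 0.34 / 0.38 | 0.374 | 0.370 (-0.004) | 0.379 (+0.005) |
| 0.5 | -0.4 | 0.33 / 0.38 | 0.367 | 0.370 (+0.003) | 0.379 (+0.012) |
| 1.0 | 0 | 0.37 / 0.47 | 0.375 | 0.334 (-0.041) | 0.363 (-0.012) |
| 1.0 | -0.2 | 0.38 / 0.47 | 0.364 | 0.339 (-0.025) | 0.368 (+0.004) |
| 1.0 | -0.4 | 0.38 / 0.47 | 0.351 | 0.339 (-0.012) | 0.369 (+0.018) |

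The extremes are -0.041 / 0.375 = -11% and +0.018 / 0.351 = +5%. With no true arm difference, both adjusted coefficients stayed within 0.003 of zero.

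**3. Effect on power.** Putting the worst-case coefficients into the formula above (n = 105, SD 1, standard error held fixed) gives 0.775 unadjusted, 0.676 adjusted by pooled regression and 0.750 adjusted with a random intercept.

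**The case against.** The strongest reply is that the SAP already specifies the unadjusted model. It repeats the maintenance paragraph without this one sentence and derives neither covariate. On that reading nothing needs to change except the protocol. This largely stands as a reading of SAP 6.3 and 6.4. But neither document says which governs, the SAP does not say that the rule was dropped, and Table 4 leaves its covariates unnamed.

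A second reply is that separating the lasting effect of the study treatment from later outside treatment is a legitimate question, and that the covariate rule removes nobody from the intention-to-treat sample. Both points are fair. The difficulty is that no such estimand is stated, and ordinary covariate adjustment does not generally deliver it when starts depend on earlier disability.

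A third concerns size. A reader might infer that adjustment must shrink FIT's advantage, perhaps by as much as a fifth. The documents do not support that. Losses of that order need steeper assumed dependence on disability and pooled regression, whereas both maintenance paragraphs name a longitudinal SEM, to which the random-intercept fit is closer. With log-odds up to 1.5 per SD, benefits up to 0.6 SD and within-person correlation of 0.6 or 0.8, pooled regression ranged from about +4% to -26%. The random-intercept fit lost about 1% to 6% when the new treatment did nothing and could gain up to about 15% when it worked. Pooled figures cannot be ruled out altogether, because the opening of SAP 6.3 names GEE for the primary and secondary aims and gives no working correlation.

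**Conclusion.** The firm finding is a discrepancy between the documents: protocol 3.F, 5.F and 5.H adjust the maintenance models for post-randomisation treatment, and SAP 6.3 and 6.4 do not. The bias is conditional. It arises only if the protocol version is run and if starting treatment depends on disability that the arms have changed. Its size and sign are unknown. Under the assumptions in the table it was about -0.04 to +0.02 SD against 0.38 SD; it was zero when starts were unrelated to disability, and it would be larger if the arms differed more in treatment-seeking.

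A reader might also infer that the trial's main result is compromised. It is not: the covariates are confined to the maintenance analyses, so the 3-month primary comparison is untouched. The point is worth settling because neither document plans the unadjusted maintenance analysis explicitly alongside an adjusted one, and Aim 1b is planned with power of only about 0.80 at a 0.38 SD gap.

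**What to change.** Reconcile protocol 3.F, 5.F and 5.H with SAP 6.3, 6.4 and Table 4:

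- State in both documents that the main analysis for maintenance of FDI (SAP H2a/b) and pain (SAP H4c/d) compares randomised arms without post-randomisation covariates.
- Report medication changes and non-pharmacologic treatment during follow-up by arm and visit.
- Keep any covariate-adjusted model only as a labelled supplementary analysis. State its estimand, and use one definition of the medication variable in place of the two in 3.F and 5.F.
- Name the covariates behind the adjusted means in Table 4.

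The cost is wording in two documents and one descriptive table. Protocol 3.F already has the treatment information recorded at each maintenance visit, so no new data are needed.

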5.	Tampa Scale of Kinesiophobia: 11-item self-report measure developed to assess fear of movement related to fear of pain and consisting of two subscales, activity avoidance and somatic focus.	ophobia: 11-item self-report measure developed to ent related to fear of pain and consisting of twoXXidance and somatic focus.XX					
6.	Child Depression Inventory (CDI-2): 27-item well validated instrument assessing self-reported symptoms of depression in adolescents for the past two weeks.	Х	Х	Х	Х	Х	
7.	Physical Activity Levels: objectively assessed using a hip-mounted omnidirectional accelerometer ** (Actigraph) for one week which yields information on daily activity counts, peak activity and time spent in sedentary, mild, moderate and vigorous activity each day.		Х	Х			
8.	NIH PROMIS Measures: 8-item short form of the PROMIS Pediatric Pain Interference Scale, 10-item Fatigue Scale, and 8-item Pain Behavior Scale.	Х		Х	Х	Х	
9.	Adverse Events (AE): Will be documented using an AE symptom checklist arranged by body system, rating of severity and relationship to treatment as in our previous trial.	Х	Х	Х	Х	Х	
10.	Therapeutic Factors Inventory (TFI-A) -Participants and Therapists: The participant measure is a short 10 item self-report measure to assess participant's experiences in the group sessions using a 5 point scale. The therapist version is a 1-item measure evaluating the overall group cohesiveness on a 5-point scale.			Х			
11.	COVID Impact. A 12-item subscale from the COVID-19 Adolescent Symptom & Psychological Experience Questionnaire (CASPE) ¹² will be used to assess the impact of COVID-19 restrictions in social, school and family domains. Participants rate the concerns they have in each of these areas on a 5- point Likert scale.	x		х	х	Х	

¹ If active treatment is delayed, and the baseline assessment is 6 or more weeks from Session 1, re-administer the FDI and VAS rating on FDI form prior to randomization.

² Accelerometry data collection was temporarily ceased in March 2020 due to restrictions regarding the COVID 19 pandemic; it was piloted again in Cincinnati for cohort 11. Accelerometry was removed from the study procedures permanently in October 2021.
 ³ Participants randomized after 11/22/22 will not complete the 9- and 12-month follow up (T6 and T7).

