*Biomechanical assessments will take place at four of seven sites (Cincinnati, Columbus, Connecticut and Boston) that have fully equipped and compatible motion/gait labs.

Gait and Balance: Quantitative assessments of functional movements will be performed using a standard gait analysis for walking at both a self-selected and prescribed speed (1.2 m/s) using a 10 camera, real-time, high speed, 3-D motion analysis system (Eagle, Motion Analysis Corp.,

Santa Rosa, CA). Assessment of landing techniques will be performed with the same 3-D motion analysis system. The subjects will land from a 31 cm box with both feet contacting separate force platforms. We have successfully used similar methodology to objectively report patient outcomes following rehabilitation, surgery, and neuromuscular training (and these tests have posed no safety concerns in these samples).

Balance/stability will be assessed using the Star Excursion Balance Test which is a functional screening tool to assess lower extremity dynamic stability, motor rehabilitation progress, assess deficits following injury and identify those at risk for lower extremity injury.

Strength: Bilateral strength assessments will be performed with an isokinetic dynamometer (Biodex Medical Systems, Shirley, NY). Peak quadriceps and hamstrings force output will be recorded during ten knee flexion/extension repetitions for each leg at 300°/second. Peak hip abduction force output will be recorded during hip abduction.¹³ The tests used for assessment of gait, balance and fitness have been validated for use in healthy adolescent populations.

** Accelerometry

Participants will be given a hip mounted accelerometer (Actigraph) for activity monitoring at 3 timepoints during the study (T1, T3, and T4). Prior to each assessment, participants will be asked to wear the device for 24-hours a day for 7 consecutive days - except when bathing, swimming or showering. For T1 the Actigraph will be given to participants at the first treatment session. For T3, the Actigraph will be given to paticipants at the last weekly treatment session, and for T4, the Actigraph will be mailed to participants then collected at T4. The Actigraph is a small, non-obtrusive, objective and sensitive measure of physical activity. We successfully used the identical procedures for activity monitoring in our completed clinical trial of CBT for juvenile fibromyalgia.

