Tests of the mechanisms that influence functional disability and pain intensity outcomes will be conducted using a multiple path mediation analyses. 1) All possible indirect pathways between psychological mechanisms (coping skills, decreased fear of activity, adherence) and physical assessments (biomechanics, physical activity and physical fitness) with the outcomes of functional disability and pain intensity will be tested for statistical significance within each of the three (FIT, CBT & GAE) groups via bias-corrected bootstrap testing of all indirect pathways, and 2) The magnitudes of the indirect effects will be tested for statistically significant differences between the three treatment groups via a multiple-group analysis. The False Discovery Rate will be used to maintain the nominal Type-1 error rate for all indirect effect tests.

J. Sample size and rationale (Power calculation)

The primary outcome for this RCT is reduction in functional disability. As such, the power calculations provided below are for the ability to detect whether FIT Teens results in significantly greater reduction in disability for Aims 1a, 1b and 1c.

Aim 1a. Differences between groups at the 3-month primary endpoint.

Power was calculated via the external Monte Carlo simulation capabilities in Mplus in two steps. First, 5000 dataset replications of hypothetical FDI scores were generated in a multiple group SEM format assuming: 1.) standardization of FDI scores, 2.) no differences in the three groups at baseline due to randomization (d = 0), 3.) group differences in FDI scores at 3 months, consistent with effect sizes from prior studies as follows: GAE (d = 0.40), CBT (d = 0.52), & FIT (d = 0.90), and 4.) N = 420 minus 20% attrition makes N = 336 (n = 112 per group) available for analysis assuming proper missing data handling. Second, the 5000 Monte Carlo replications were then analyzed using a longitudinal SEM assuming linear trend (i.e., slope loadings coded 0, 2, & 3) with dummy-coded CBT & GAE groups (FIT = reference). Results showed power ≥ 0.80 if the standardized 'slope on group' coefficient for either CBT or GAE is $\beta > 0.12$ assuming proper handling of cluster by site nesting as described above. With a revised sample size of N=315 (n=105 per group), our recalculated power analysis estimates power of >.80 for the GAE arm (versus reference group) and .79 for the CBT arm.

Aim 1b. Maintenance of treatment gains over follow-up.

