## 4.0 Power and Sample Size Estimates

(Note: the following power calculation is an amended version from the original power calculation and based on the R01 Ancillary Funded Award in February 2023 which reduced the scope of the RCT to accommodate delays due to the COVID19 pandemic)

The primary outcome for this RCT is reduction in functional disability. Power was determined for the ability to detect whether FIT Teens results in significantly greater reduction in FDI scores for Aims 1a, 1b, and 1c. Assumptions for power calculations were based on previous research showing statistically significant decreases in disability resulting from CBT (Cohen's d = .52) and GAE (Cohen's d = .40) interventions (6,7) and our pilot studies showing stronger post-treatment effect sizes for FIT Teens (d = .95 - 1.22). Power estimates were calculated with more conservative effect sizes for FIT Teens (i.e., d = .90). All power calculations were based on the assumption of 20% attrition and proper handling of missing data.

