# 6.5 Exploratory Analyses

Mechanistic models of how treatment-related improvements in psychological (coping, fear of movement, adherence) and physical factors (objectively measured physical activity, biomechanical changes and fitness) explain changes in disability and pain outcomes across the three groups will be examined on an **exploratory basis**. Multiple path mediation analyses. 1) Selected indirect pathways between psychological coping skills, decreased fear of activity, and improved biomechanics (predictors), physical activity engagement and physical fitness (mediators), and functional disability and pain intensity (outcomes) will be tested for statistical significance within each of the three (FIT, CBT & GAE) groups, and 2) The magnitudes of the indirect effects will be tested for statistically significant differences between the three treatment groups. The False Discovery Rate will be used to maintain the nominal Type-1 error rate for all indirect effect tests.

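### The mechanism tests use the bias-corrected bootstrap within arms of about 84 to 105; it over-rejects when one path is zero and the other moderate or large, so the stated error control is not assured

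*Protocol*

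**What the plan says.** Protocol 5.I (Exploratory Aim) describes a multiple-path mediation analysis. It links psychological mechanisms and physical measures with functional disability and pain, and tests each indirect effect separately within FIT, CBT and GAE by "bias-corrected bootstrap testing of all indirect pathways". A second step compares the indirect effects between arms. The section closes: "The False Discovery Rate will be used to maintain the nominal Type-1 error rate for all indirect effect tests". Protocol 5.C and SAP 6.0 (Statistical Analyses) set alpha at 0.05, two-sided.

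SAP 6.5 repeats the FDR sentence but differs in two ways. Its set of tests is "Selected indirect pathways between psychological coping skills, decreased fear of activity, and improved biomechanics (predictors", with physical activity and fitness as mediators and disability and pain as outcomes. It also names no bootstrap variant. SAP 6.1 mentions bootstrap resampling only in general terms.

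On size, Protocol 5.J reads "With a revised sample size of N=315 (n=105 per group", and SAP 4.0 states "All power calculations were based on the assumption of 20% attrition and proper handling of missing data". Protocol 4.A adds that "Biomechanical assessments will take place at four of seven sites" and "Accelerometry was removed from the study procedures permanently in October 2021", so some pathways have fewer patients than the arm total.

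**The concern.** An indirect effect is a product of two paths, a × b. It is null if either path is zero. The bias-corrected bootstrap shifts the interval limits by an estimate of the median bias of a × b. In samples of this size that shift can make the interval exclude zero too often when one path is zero and the other is clearly not.

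An FDR procedure counts tests; it does not repair p-values that are too small. If the single tests reject more than 5% of true nulls at nominal 5%, the FDR step inherits the excess. The trial could then report mechanisms of FIT Teens under an error guarantee that the named test does not deliver. No primary or secondary conclusion depends on this analysis.

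**Working it through.** **Inputs from the documents.** Bias-corrected bootstrap within arm (Protocol 5.I). Alpha 0.05, two-sided (Protocol 5.C). n per arm = 315 / 3 = 105 (Protocol 5.J). If 105 is the number randomised, 20% attrition (SAP 4.0) leaves 105 × 0.80 = 84. For biomechanics at four of seven sites, equal recruitment would give 105 × 4/7 = 60.

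**Assumed, because the documents are silent.** Path sizes; a single-mediator model X → M → Y with normal errors of variance 1 and no direct effect; independent patients (no cohort or site clustering); FDR level q = 0.05; and a family of 3 psychological × 3 physical × 2 outcomes = 18 tests for one arm.

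**Method.** Let t be the estimate of a × b and t* its resampled values.
- Bias correction: z0 = Φ⁻¹(share of t* below t).
- Bias-corrected 95% limits: the quantiles of t* at Φ(2·z0 − 1.96) and Φ(2·z0 + 1.96).
- Percentile 95% limits: the 2.5% and 97.5% quantiles of t*.
- Reject if the interval excludes zero.

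Each cell has 3,000 trials of 1,000 resamples. The Monte Carlo standard error at a rate of 8% is √(0.08 × 0.92 / 3000) = 0.005.

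**Step 1: rejection of true nulls, nominal 5%.** Where two figures are given, the first has a = 0 and the second b = 0.

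| Non-zero path | BC, n = 105 | Percentile, n = 105 | BC, n = 84 | Percentile, n = 84 |
|---|---|---|---|---|
| none | 0.5% | 0.1% | 0.9% | 0.3% |
| 0.14 | 2.9%, 3.6% | 1.1%, 1.4% | 3.1%, 3.1% | 1.3%, 1.2% |
| 0.26 (a = 0 only) | 7.3% | 3.8% | 7.2% | 3.7% |
| 0.39 | 7.4%, 8.5% | 5.3%, 5.7% | 7.5%, 8.1% | 4.6%, 5.2% |
| 0.59 | 7.4%, 7.6% | 5.6%, 6.1% | 8.4%, 7.5% | 6.5%, 5.8% |

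Separate runs at a path of 0.3 and n = 105 gave 7.5 to 8.3% for the bias-corrected test and 4.2 to 5.3% for the percentile test. A path of 0.15 gave 4.2% for the bias-corrected test. At n = 50 the bias-corrected rate was 1.6 to 2.0% at 0.14, 4.8% at 0.26, and 7.4 to 9.0% at 0.39 to 0.59.

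**Step 2: achieved FDR after Benjamini-Hochberg at q = 0.05.** n = 105, non-zero paths 0.39, tests drawn independently, 4,000 resamples. The bias-corrected p-value is 2·[1 − Φ(|2·z0 − p0|)], where p0 = Φ⁻¹(share of t* below 0).

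| Family | BC | Percentile |
|---|---|---|
| 2, 6 or 18 tests, all one-path nulls | 7.9%, 8.5%, 7.9% | 5.4%, 4.6%, 4.3% |
| 18: 6 real, 12 one-path nulls | 5.8% | 3.6% |
| 18: 6 real, 6 one-path, 6 both-zero | 2.9% | 1.8% |
| 18: 12 real, 6 one-path | 2.8% | 1.7% |
| 18: 6 one-path, 12 both-zero | 2.7% | 1.3% |
| 18: all both-zero | 0.0% | 0.0% |

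**Step 3: cost in power.** With a = b = 0.3 and before any FDR step, moving from the bias-corrected to the percentile test lowers power from about 0.81 to 0.74 at n = 105, and from about 0.48 to 0.37 at n = 60.

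**The case against.** The strongest reply is that the excess is conditional. It needs one path absent and the other at least moderate, and nothing in the documents says how often that occurs. For small paths the test is at or below nominal, and with both paths zero it hardly ever rejects. In four of the six family types tried, the achieved FDR stayed at or below about 3%. The analysis is labelled exploratory, and the percentile method costs power and is conservative for small paths. All of this stands. It limits the point but does not remove it, because the protocol makes an unconditional statement about error control.

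Three stronger readings are tempting, and the documents do not support them.
- A reader might infer that the FDR step can never hold its level here. Step 2 shows that it depends on the mix of nulls.
- A reader might infer that one-path nulls are likely because coping, fear, fitness, disability and pain change together. Joint change points rather to both paths being non-zero, and then rejection is not an error.
- A reader might infer from the SAP's narrower set that pathways could be picked by their p-values. SAP 6.5 restricts them by role (predictor, mediator, outcome) and describes no selection on results. The absent list is missing detail, not evidence of selective testing.

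It is also fair to say that only the protocol names the bias-corrected method. SAP 6.5 is silent and does not withdraw it, so the protocol's method is the only one specified.

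**Conclusion.** The point holds in a limited form. With 84 to 105 patients per arm, the bias-corrected bootstrap rejects about 7 to 8.5% of true nulls at nominal 5% when one path is zero and the other is about 0.3 or larger. The FDR step can then run at about 8% in the worst family tried, and at 5.8% when one-path nulls are two thirds of the family. In the other mixes it stays at or below its level, so the stated control is not assured rather than impossible.

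This rests on assumed path sizes, a simple mediation model, independent tests and no clustering. A smaller point of wording: FDR bounds the expected share of false discoveries, which is not the same as a Type-1 error rate for each test. The importance is low because the aim is exploratory.

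**What to change.** In Protocol 5.I, replace the bias-corrected bootstrap with the percentile bootstrap, and name the same method in SAP 6.5 so that the two documents agree. For paths of about 0.3 to 0.5 this brings the single-test rate to about 4 to 6.5% at n = 84 to 105. That is close to nominal, though not exact.

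The change is one option in the software and one phrase in each document. It needs no new data and touches no clinical procedure. The cost is the loss of power in Step 3, which weighs most on the biomechanics pathways, where n is smallest. Part of that apparent loss is the excess rejection being removed.
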